The efficacy of Dotarem enhanced late gadolinium enhancement (LGE) imaging has been investigated and compared to gadobutrol (Gadavist, Bayer, Germany) to visualize and quantify myocardial scar.¹³ However, a similar comparison for the assessment of myocardial ischemia by CMR myocardial perfusion – an even more crucial step in a clinical CMR protocol – would further strengthen the value of Dotarem in cardiovascular imaging. While LGE is able to visualize irreversible myocardial injury, myocardial perfusion imaging has the ability to depict reversible ischemia that can potentially be treated by coronary intervention.

C. PRELIMINARY STUDIES

Our research group consists of clinical and research faculty who have extensive experience and a substantial publication record related to contrast enhanced cardiac MRI and contrast agent characterization.¹⁴⁻¹⁸ In a previous research project, our team developed an image analysis technique (detailed in Section D) that we will use in Aim 2 to investigate the relaxation profile of Dotarem.¹⁶

D. RESEARCH DESIGN AND METHODS (INCLUDING DATA ANALYSIS)

D.1 IMAGE ACQUISITION

This prospective study will include a total of 90 patients (Aim 1 + Aim 2) who present to the MUSC Radiology Department for a clinically indicated cardiac MRI scan over a 2-year period. Patients will be imaged using a state of the art 1.5T scanner (MAGNETOM Avanto, Siemens Healthcare, Erlangen, Germany) system.

Aim 1: In this specific aim, a total of **60 patients** referred for a clinically indicated stress myocardial perfusion MRI scan out of concern of suspected myocardial ischemia will be included. Patients will be scanned using a **standard clinical contrast-enhanced stress perfusion protocol** (regadenoson 0.4mg bolus) detailed in Figure 1. Patients will be randomized into two groups prior to patient consenting: **Group 1 (n=30)** will receive the **clinically approved gadoterate meglumine** (Dotarem, 0.1mmol/kg) as contrast agent for their clinical perfusion study, while **Group 2 (n=30)** will receive the **clinically approved gadobutrol** (Gadavist, 0.1mmol/kg) as contrast agent. The contrast agents will be administered at a flow rate of 5.0 ml/s for both groups. In this study aim, all imaging protocols will comply with standard of care and only the perfusion data will be post-processed and analyzed.

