Aim 2: In this specific aim, a total of **30 patients** referred for a clinically indicated contrast enhanced cardiac MRI will be included. These patients will undergo a **clinical viability cardiac MRI protocol** with the administration of **gadoterate meglumine** (Dotarem, 0.1mmol/kg), except that a **prototype MRI T1 mapping pulse sequence** will be used to acquire equilibrium T1 maps during the first pass of the contrast agent. This first pass perfusion step will be performed in rest, no stress agent will be administered. The rest perfusion acquisition is part of the standard protocol, however, we will use this prototype pulse sequence for research purposes.

[figure not shown]

Figure 1 – MRI protocols

D.2 IMAGE ANALYSIS

In Aim 1, we will generate signal intensity-time curves from the perfusion data and evaluate the characteristics of signal intensity changes and absolute myocardial blood flow using the MASS Research Software (LUMC, Leiden, Netherlands). The signal characteristics will be compared between the two contrast groups. Image quality will also be subjectively rated by multiple independent observers.

In Aim 2, we will generate equilibrium T1 maps based on the pre-contrast T1 and repeated inversion recovery images during the perfusion of the CA. This technique allows the calculation of the post-contrast T1 at every phase during the first-pass perfusion of the CA. The uniformity of T1 and R1 (inverse T1) will be evaluated using the MASS Research Software.

D.3 STATISTICAL METHODS / SAMPLE SIZE JUSTIFICATION

All analyses and graphs will be performed by using commercially available software (MedCalc version 12.7.2; SPSS version 21). Descriptive statistics will be provided as mean \pm standard deviation (SD) for continuous variables and absolute and relative frequencies for categorical variables. Normal data distribution will be assessed with a Kolmogorov-Smirnov test. For each group, comparisons of patient characteristics will be performed by using the χ^2 test for categorical variables and t-test or Mann-Whitney-U-test for continuous variables as appropriate. Subjective image quality scores will be compared using the χ^2 test with the Yates continuity correction for categorical variables and inter-observer agreement for image quality will be calculated using Cohen kappa statistics and interpreted as follows: ≤ 0.20 slight or poor agreement, $0.20-0.40$ fair agreement, $0.40-0.80$ moderate agreement, ≥ 0.80 excellent agreement.

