E. PROTECTION OF HUMAN SUBJECTS

E.1 RISK TO THE SUBJECTS

E.1.a Human Subject Involvement and Characteristics

Aim 1

Inclusion criteria:

To be eligible for the study: (All answers must be “YES” for subject to be eligible.)

1. Subject must be referred for a clinically indicated contrast-enhanced stress myocardial perfusion MRI scan out of concern of suspected myocardial ischemia.
2. Subject must be older than 18 years of age.
3. Subject must provide written informed consent prior to any study-related procedures being performed.
4. Subject must be willing to comply with all clinical study procedures.

Exclusion Criteria:

The presence of the following excludes subjects from the study: (All answers must be “NO” for subject to be eligible.)

1. Subject is a pregnant or nursing female. Exclude the possibility of pregnancy:
 - By testing (serum or urine beta HCG) within 24 hours before study date, or
 - By surgical sterilization, or
 - Post-menopausal, with minimum one (1) year history without menses.
2. Subject has an implanted cardiac pacemaker or implantable defibrillator.
3. Subject has a ferromagnetic vascular clip.
4. Subject has a neurostimulation system (e.g. TENS-Unit).

5. Subject has any type of cochlear implant.
6. Subject has ocular foreign body (e.g. metal shavings).
7. Subject carries any implanted device (e.g. insulin pump, drug infusion device).
8. Subject has shrapnel, bullet, or other type of metal fragments within the body.
9. Subject has an acute psychiatric disorder or is cognitively impaired.
10. Subject is using or is dependent on substances of abuse.
11. Subject is unwilling to comply with the requirements of the protocol.
12. Subject is in acute unstable condition.
13. Subject has an allergy against gadolinium based contrast agents or pharmaceutical stressors used in this study.
14. Subject has impaired renal function (creatinine > 1.5 mg/dl).
15. Subject presenting with acute coronary syndrome.
16. Positive cardiac enzymes positive troponin, CK-MB, or myosin
17. ST-elevations, new transient ST changes greater than 0.05mV or T- wave inversions with symptoms

Aim 2

Inclusion criteria:

To be eligible for the study: (All answers must be “**YES**” for subject to be eligible.)

1. Subject must be referred for a clinically indicated contrast-enhanced stress myocardial perfusion MRI scan out of concern of suspected myocardial ischemia.
2. Subject must be older than 18 years of age.

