The research materials that will be obtained from living human subjects are: the MR images, report, injection report, progress notes, medication records, vital signs, medical history and demographics, and all other applicable clinical information.

The Principal Investigator, Sub-Investigator(s) and the Study Coordinator(s) will be the only personnel who will have access to subject identities, with the exception of any regulatory personnel (MUSC IRB auditors, etc.). All subject identities will be removed prior to publication.

Contrast and Drug Management

Contrast agents (Dotarem and Gadavist) and stress agent (Regadenoson) will be ordered and dispensed from the MUSC inpatient pharmacy per clinical protocol.

E.1.c Potential Risks

Vein puncture

Patients could experience bruising, pain, and rare incidence of infection at the vein puncture site. This is like a blood test. This puncture is used to inject the contrast agents. Care will be taken to avoid these possible risks. Skin or vein irritation, fainting, blood clot formation, bleeding at the injection site, or an infection could also occur.

Adverse reactions caused by gadolinium contrast agent

Gadolinium contrast agent will be administered as part of the clinical protocol, independently from the research component of the study. The research protocol will not increase the risk of contrast related adverse reactions in any of the research aims. Despite excluding patients with known history of allergy

to gadolinium-based contrast material, there is a small risk that a patient will have an allergic reaction to contrast medium. In this event, the attending physician supervising the MRI acquisition in the study will administer appropriate care. In patients with pre-existing renal dysfunction, gadolinium-based contrast material may cause further deterioration in renal function. Therefore, patients with decreased renal function (more than 1.50 mg/dL serum creatinine) will be excluded from this study.

Risks from Contrast Agent Extravasation

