Although extremely rare, it is possible that an IV needle is not properly located within the vein or becomes dislodged when the patient lies down on the examination table. When contrast material is injected, it may then leak into the surrounding tissue. This can be painful and in very few instances has been reported to cause pressure on underlying nerves or vessels that needs to be surgically relieved. Usually, however, a contrast media extravasation is noticed early on by the personnel monitoring the procedure. However, even if a full dose of contrast material is injected in the tissue surrounding a vein, permanent damage is extremely unlikely. Usually the contrast material is fully absorbed by the body within a day without any harmful effect. In addition, in our department we use the latest automated contrast media injector generation, which also comprises of an automated extravasation detection device attached to the arm of the patient. Since the implementation of this device we have not experienced any major extravasation of contrast material.

Adverse reactions caused by stress agent administration

The following reactions are listed as warnings and precautions when using regadenoson (Lexiscan): Myocardial ischemia, sinoatrial and atrioventricular nodal block, hypotension, bronchoconstriction. The following adverse reactions associated with regadenoson are considered transient and are listed in the package insert: dyspnea or urge to breathe deeply, headache, flushing, chest discomfort, angina pectoris or ST segment depression, lightheadedness/dizziness, chest pain, nausea, abdominal discomfort, impaired taste, feeling hot. In addition, dyspnea can occur during stress myocardial perfusion imaging with associated arrhythmias such as hypoxia induced bundle branch block. The first signs of these rare side effects will cause the termination of the examination. Note, that stress agent will not be administered for research purposes.

Risk of metal objects in the body

Patients may suffer bodily harm in the course of the MRA examination from having metal objects in their clothing, from metal implants (e.g. pacemaker, implanted defibrillator, cochlear implants, cerebral aneurysm clips), or any other metal within the body (shrapnel, bullet or metal fragments). Before patients undergo the procedure, they will be prompted to take out any metal objects. Patients will be asked a series of detailed questions about any metal that they may have their body.

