Acquisition of patient information

The risks associated with gathering this information are believed to be very low. This information will be stored on a password-protected computer and network server and in a locked office (ART Cardiac Imaging Research Office). The data from this study will be accessible only to the team of researchers from this application.

E.2 ADEQUACY OF PROTECTION AGAINST RISKS

E.2.a Recruitment and Informed Consent

Patients who have been referred for a stress myocardial perfusion MRI (Aim 1) or myocardial viability MRI (Aim 2) as part of a standard clinical evaluation determined by the treating physician(s) will be eligible for the study and recruited from the MUSC MRI schedule. The MRI technologist or member of the nursing staff will speak with potential subjects to ensure their willingness to be approached by a member of the research team. Willing patients will be approached and will undergo the informed

consent process. Consented subjects will undergo their clinically indicated MRI using the standard stress protocol (Aim 1) or the modified viability protocol (Aim 2).

Patients will be screened by approved study personnel from the MUSC MRI schedule under a HIPAA waiver. Study eligibility determination and study enrollment will be assessed and performed by and investigator in concert with a study coordinator delegated by the PI and approved by the IRB as being authorized to obtain informed consent.

The PI, Sub-I(s) or the Study Coordinator(s) will obtain informed consent prior to enrollment into the study. The subject will be taken to a quiet/private area (which may include the scanning room, the patient bays or other private areas) and the study purpose, procedures, duration, risks/discomforts, benefits, alternatives, new information procedures and privacy statements will be explained to the subject.

The subject will be asked to verbally repeat pertinent study information to ensure subject understands the nature of the research. Subjects will be provided the opportunity to ask any questions they may have. Consent will be documented in the currently IRB approved version of the informed consent and will be signed and dated by the person obtaining informed consent and the subject.

E.2.b Protection against Risk

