To minimize the risk of post-contrast nephropathy, patients with decreased renal function (creatinine >1.5 mg/dL) will not be eligible for this study. To minimize the risk of allergic reactions to gadolinium contrast material, patients with a history of allergic reactions to gadolinium contrast material will also be excluded.

All subjects' medical records will be confined in the usual medical health information office according to their policies and procedures. Each staff member that has approved access to electronic medical records will be given their own password and will be instructed not to reveal that password to anyone else. In addition, those copies of subject information utilized for the research protocol will be kept locked in the Radiology Research suite (ART 2244) in a research specific folder that will identify the subject on the outside of the folder only by initials, subject code (subsequent subject identifiers, i.e. 001, 002, 003, etc., this number will not be able to identify the subject), protocol name, and IRB study number (Pro #). Any data that are used in publication, analyses, etc. will not identify the subject by name, etc. Subjects will be monitored in clinic as per clinical standard practice for any possible side effects and treated as indicated.

E.3 POTENTIAL BENEFITS OF THE PROPOSED RESEARCH TO THE SUBJECTS AND OTHERS

The subjects whose data, documents, and records will be reviewed are not likely to receive any benefit from the proposed research. However, the quantitative and qualitative evaluation of myocardial perfusion has an important role in patient diagnosis, therapy and prognosis. The improved and more reliable detection of myocardial perfusion defects may provide faster diagnosis and better patient management, as well as avoid unnecessary tests (including invasive procedures and radiation exposure). As of today, Dotarem is the only gadolinium-based contrast agent without any reported nephrogenic systemic fibrosis case. Broadening the clinical use of Dotarem towards the cardiac MRI field would provide substantial benefit to patients, especially those who suffer from pre-existing renal disease.

E. 4 IMPORTANCE OF THE KNOWLEDGE TO BE GAINED

Clinical stress myocardial perfusion MRI is a contrast enhanced acquisition that requires the administration of gadolinium-based contrast agent. Currently, there is no FDA label exist for such

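### Aim 1 patients are randomised before consent with no concealment described, so patients can be lost differently by arm after allocation

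*Combined protocol and SAP*

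**What the plan says.** Section D.1 (Image Acquisition, Aim 1) plans 60 stress perfusion patients, 30 to Dotarem and 30 to Gadavist, and fixes the order: "Patients will be randomized into two groups prior to patient consenting".

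Section E.1.a, Aim 1 inclusion criterion 3, reads: "Subject must provide written informed consent prior to any study-related procedures being performed". Criterion 4 adds willingness to comply. Some exclusions need judgement, such as an acute unstable condition or unwillingness to follow the protocol.

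Section E.2.a (Recruitment and Informed Consent) describes schedule screening under a HIPAA waiver, a check by a technologist or nurse that the patient may be approached, consent, and then the scan. It states "The PI, Sub-I(s) or the Study Coordinator(s) will obtain informed consent prior to enrollment into the study" and "Study eligibility determination and study enrollment will be assessed and performed by and investigator in concert with a study coordinator". It does not mention randomisation.

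Section D.3 says "For each group, comparisons of patient characteristics will be performed" and plans no adjusted analysis. No section covers how the sequence is generated, who holds the list, whether the assignment is concealed, or how patients who are allocated but not enrolled are counted.

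**The concern.** Randomisation protects a comparison only if whatever decides who enters the analysis is settled before the assignment can be known, or independently of it. D.1 puts the assignment first. If those who approach, screen and consent patients can see the agent, refusals and exclusions may differ by arm. Aim 1's claim that Dotarem is not inferior to gadobutrol would then rest on groups partly formed by selection. Measured imbalance might show in the D.3 comparison of characteristics; unmeasured imbalance would not.

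A second issue is internal consistency. A random choice of agent made for the study comes before consent, while criterion 3 puts consent before anything study-related.

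**Working it through.** **Order of events.** Set side by side, the sections give this sequence for Aim 1:

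1. Randomisation, before consent (D.1).
2. Consent, before enrolment (E.2.a), with consent and willingness both eligibility criteria (E.1.a, criteria 3 and 4).
3. Eligibility and enrolment, settled by an investigator with a coordinator (E.2.a). Section F places the serum creatinine test, which decides exclusion 14, in the Radiology patient bays during patient preparation, so eligibility may still be open close to the scan.
4. The scan.

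Schedule screening and the check of willingness to be approached also precede consent, but no section places them relative to randomisation. Consent and final eligibility can therefore remove a patient after step 1. Concealment would make this largely harmless, but none is described. The omission is not explained by the missing figure, which is captioned as showing MRI protocols.

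**Criterion 3.** If random assignment for the study is a study-related procedure, D.1 and criterion 3 conflict. If placing a patient on a list is not a procedure, allocating, consenting and then scanning satisfies both. The term is undefined, so the text does not settle the matter.

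**E.2.a.** Consent before enrolment is literally compatible with D.1 if enrolment means entry after consent. E.2.a omits the randomisation step; it does not contradict it.

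**Counts.** The plan's own totals agree: 30 + 30 = 60 for Aim 1, and 60 + 30 = 90 with Aim 2. It gives no consent rate, so the rates c below are assumptions.

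- If 30 per group counts consented patients, the number to allocate per arm is 30/c, rounded up. c = 0.90: 33.3, so 34, or 68 in all and 8 not enrolled. c = 0.80: 37.5, so 38, or 76 and 16. c = 0.70: 42.9, so 43, or 86 and 26.
- If 30 per group counts randomised patients, the number left per arm is 30c: 27, 24 or 21.

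The plan does not say which count is meant.

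**Illustrative shift (all inputs assumed).** Suppose half of the patients have severe disease and consent is 80% everywhere, except among severe patients in one arm, where it is c. The severe share in that arm becomes 0.5c/(0.5c + 0.4): 0.35/0.75 = 0.467 for c = 0.7, 0.30/0.70 = 0.429 for c = 0.6, and 0.25/0.65 = 0.385 for c = 0.5. The other arm stays at 0.500, so the differences are 0.033, 0.071 and 0.115. If severe and other patients differ by 0.5 to 1.0 SD on the endpoint, the shift runs from 0.033 × 0.5 = 0.017 SD to 0.115 × 1.0 = 0.115 SD. The standard error of a difference at 30 per arm is √(2/30) = 0.258 SD, so the largest shift is 0.115/0.258 = 0.45 of a standard error. Its sign depends on which arm loses the patients and on how the endpoint relates to disease.

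**The case against.** The best defence is that the authors regard agent and scan as clinical care. D.1 says that Aim 1 imaging follows standard of care and that only the perfusion data are analysed. E.1.c says that contrast is given under the clinical protocol, independently of the research. On that view allocation is bookkeeping before consent, and criterion 3 is met. This stands as a possible reading, and it is why the passages need reconciling. It does not remove the risk of selection, which depends on the order and on concealment, not on who would have ordered the contrast.

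Many exclusions are also objective (implants, creatinine, a pregnancy test). That narrows the opportunity without closing it, because consent and the judgement-based criteria remain.

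Four stronger readings are tempting, and the documents do not support them:

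- *That the protocol breaches its own consent rule.* This depends on an undefined term.
- *That enrolling staff know the assignment.* The documents are silent; they say neither that staff know nor that they do not.
- *That staff would favour one arm because E.3 says* "Dotarem is the only gadolinium-based contrast agent without any reported nephrogenic systemic fibrosis case". E.3 ties the benefit especially to patients with pre-existing renal disease, and patients with creatinine above 1.5 mg/dL are excluded, so this motive is weak.
- *That the false-positive rate of the non-inferiority test is inflated by a stated amount.* D.3 gives no non-inferiority test, margin or alpha, so any such rate would describe a test the plan does not contain.

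A deliberate randomise-before-consent design is also conceivable, but the plan neither names nor justifies one, and the only waiver it mentions is for screening.

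**Conclusion.** The concern holds as a weakness of design that should be fixed. The order in D.1 and the absence of any described concealment are plain from the text. Following the plan as written permits selection by arm after allocation; it does not show that selection will happen. Neither size nor direction can be derived from the documents. On the assumed inputs above, the shift stays below half a standard error. That suggests a modest effect but depends wholly on those inputs. D.3 might reveal imbalance in measured characteristics, but it plans no adjustment for it. With criterion 3, the finding is an unresolved inconsistency, not a proven conflict. With E.2.a, it is an omitted step.

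**What to change.** Change D.1 to: *After written informed consent and confirmed eligibility, patients will be randomised 1:1 from a concealed list (sealed opaque envelopes or a central list), with the assignment revealed only once both are documented; n=30 per group counts consented, randomised patients, analysed as allocated.* Add the same step for Aim 1 to E.2.a.

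If blocking is used to reach 30/30, keep the block sizes in a restricted document. Printing them in a protocol that enrolling staff read would make later assignments easier to predict.

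If early allocation is kept for logistics:

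- justify it and reconcile it with criterion 3;
- conceal the assignment from those who approach, screen and consent patients until consent and eligibility are documented;
- report every allocated patient who is not enrolled, by arm and with the reason.

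The cost is a short change of wording in two sections, with no added patients or visits. The downside is practical. The protocol says "Contrast agents (Dotarem and Gadavist) and stress agent (Regadenoson) will be ordered and dispensed from the MUSC inpatient pharmacy per clinical protocol", so both agents must be at hand, or one dispensed, after consent on the scan day. The documents do not say how long dispensing takes, which is why the concealed early option is worth keeping open.

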Clinical Study Protocol

Dotarem® for Myocardial Perfusion Cardiovascular Magnetic Resonance

Principal Investigators: U. [name]

Medical University of South Carolina
Department of Radiology and Radiological Science
[name]
[name]

CONFIDENTIALITY STATEMENT

This document is the confidential property of Medical University of South Carolina, Radiology Department. No Part of it may be transmitted, reproduced, published or used by other persons without the permission of the Principal Investigator.

Dotarem® Evaluation for Myocardial Perfusion Cardiovascular Magnetic Resonance

Table of Contents

A. SPECIFIC AIMS	3
B. BACKGROUND AND SIGNIFICANCE	3
C. PRELIMINARY STUDIES	3
D. RESEARCH DESIGN AND METHODS (including data analysis)	4
D.1 Image acquisition	4
D.2 Image analysis	5
D.3 Statistical Methods / Sample Size Justification	5
E. PROTECTION OF HUMAN SUBJECTS	5
E.1 RISK TO THE SUBJECTS	5
E.1.a Human Subject Involvement and Characteristics	5
E.1.b Sources of Materials	7
E.1.c Potential Risks	7
E.2 ADEQUACY OF PROTECTION AGAINST RISKS	8
E.2.a Recruitment and Informed Consent	8
E.2.b Protection against Risk	9
E.3 POTENTIAL BENEFITS OF THE PROPOSED RESEARCH TO THE SUBJECTS AND OTHERS	9
E.4 IMPORTANCE OF THE KNOWLEDGE TO BE GAINED	9
E.5 SUBJECT SAFETY AND MINIMIZING RISKS (Data and Safety Monitoring Plan)	10
F. FACILITIES AVAILABLE	10
G. REFERENCES	10

A. SPECIFIC AIMS

The overall goal of this study is to investigate the signal intensity and relaxation rate characteristics of gadoterate meglumine (Dotarem, Guerbet, USA) enhanced myocardium during rest and stress perfusion cardiovascular magnetic resonance (CMR) compared to gadobutrol (Gadavist) to prove that Dotarem provides constantly high myocardial relaxation necessary for accurate quantitative perfusion evaluation. Within this overall goal, the following specific aims will be pursued:

- **Aim 1:** To test the hypothesis that the signal intensity enhancement during Dotarem myocardial stress/rest perfusion is relatively constant, providing linear and stable enhancement in the myocardium, and is not inferior compared to gadobutrol (Gadavist).
- **Aim 2:** To test the hypothesis that the relaxation rate enhancement during Dotarem myocardial rest perfusion is uniform in the myocardium.

B. BACKGROUND AND SIGNIFICANCE

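### D.3 gives image quality scores a Yates-corrected chi-square, a 2x2 test, without stating the scale, the cut-point or how several readers' ratings are combined

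*Combined protocol and SAP*

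**What the plan says.** D.1 allocates 60 Aim 1 patients to two parallel groups of 30, one per contrast agent ("Patients will be randomized into two groups prior to patient consenting"). D.2 adds that "Image quality will also be subjectively rated by multiple independent observers". For the analysis, D.3 says "Subjective image quality scores will be compared using the" chi-square test "with the Yates continuity correction for categorical variables".

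The neighbouring sentences in D.3 matter for reading this one:

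- For patient characteristics, "comparisons of patient characteristics will be performed by using the" plain chi-square test if categorical, and the "t-test or Mann-Whitney-U-test for continuous variables as appropriate". The rank test is thus already in the plan, but for continuous characteristics only.
- Descriptive statistics include "absolute and relative frequencies for categorical variables".
- Inter-observer agreement is summarised by Cohen's kappa.

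Neither D.2 nor D.3 gives the number of grades, a cut-point, the number of readers, a rule for combining readers, or a significance level. Both sections read as continuous text, so these gaps do not look like redactions or extraction losses.

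**The concern.** The Yates correction is defined for a 2x2 table. A subjective score may be binary, or it may have several ordered grades, and the text allows either.

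- **Ordinal.** The named test cannot be run until the grades are split in two. The plan does not say where, so the split could be chosen after the scores are seen. Any split discards the ordering.
- **Binary.** The test runs, but at 30 per group it rejects well below its nominal level and so misses real differences more often than the same test uncorrected.
- **Several readers.** On either reading the number of independent observations is 30 per group only if each patient contributes one score. The plan does not say so.

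At stake is a difference in image quality between the agents that is missed, or, if ratings are pooled, a difference declared too readily.

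**Working it through.** The plan states no size, power, effect or significance level for this comparison, so there is no figure of its own to reproduce.

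**Inputs.** From the documents: 30 per group (D.1), Yates-corrected chi-square (D.3). Assumed: two-sided 5% level (critical value 3.841), no dropout, and all scales, distributions and odds ratios below.

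**1. Binary score, one per patient.** With a and b good images of n = 30 per group, N = 60 and c = a + b, the statistic is

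X² = N·d² / [n·n·c·(N − c)], where d = |a(n − b) − b(n − a)|, reduced by N/2 = 30 for Yates.

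Exact size is the sum, over all tables with X² ≥ 3.841, of Bin(a; 30, p)·Bin(b; 30, p).

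| Common rate p | Yates | Uncorrected |
|---|---|---|
| 0.50 | 2.7% | 5.2% |
| 0.60 | 2.6% | 4.9% |
| 0.70 | 2.6% | 4.9% |
| 0.80 | 2.2% | 4.9% |
| 0.90 | 0.9% | 5.4% |

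The values are symmetric about 0.5. Over 10-90% the ranges are 0.9-2.7% and 4.8-5.5%. At a rate of 95% the Yates size falls to 0.15%. At 30 vs 30 the Yates rejection region is identical to that of Fisher's exact test. At odds ratio 3, with control rates of 50-90% and both directions, exact power is 3-45% with Yates and 15-56% without, a gap of 10-15 points.

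**2. Ordinal score, one per patient.** Assumed control distributions, worst to best grade: 10/30/60, 5/15/40/40 and 3/7/20/40/30%. The other group is shifted by a proportional odds ratio of 3.

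Example, 4 grades, shift to worse: 80% of controls are in the top two grades, odds 0.80/0.20 = 4. Then 4/3 = 1.333 and 1.333/2.333 = 57.1%. Yates power for 80% vs 57.1% is 37.9%, the best of the three possible cuts.

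Power in %, for 3/4/5 grades (Mann-Whitney and unordered chi-square simulated, Yates exact at its best cut):

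| | Shift to worse | Shift to better |
|---|---|---|
| Mann-Whitney, tie-corrected | 59.9 / 62.3 / 63.5 | 46.8 / 58.2 / 61.1 |
| Yates, best cut | 45.2 / 37.9 / 44.1 | 36.2 / 45.2 / 44.1 |
| Same cut, uncorrected | 55.8 / 48.0 / 54.7 | 46.3 / 55.8 / 54.7 |
| Unordered chi-square | 49.0 / 43.9 / 38.8 | 35.7 / 39.3 / 37.2 |
| Loss, Mann-Whitney minus Yates | 14.7 / 24.4 / 19.4 | 10.6 / 13.0 / 17.0 |

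About 10-11 points of each loss come from the correction (row 3 minus row 2). The rest, 0.5 to 14.3 points, comes from the cut (row 1 minus row 3). Mann-Whitney size on these scales is 4.9-5.0%. With even grades the loss is 15-22 points. With 80-90% of controls in the top grade it is 11-14.

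**3. Where the ranking reverses (4 grades).**

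| Difference | Mann-Whitney | Yates, best cut | Unordered chi-square |
|---|---|---|---|
| Spread only: 10/40/40/10 vs 30/20/20/30% | 6% | 37% | 78% |
| One cut only: 5/15/40/40 vs 5/15/10/70% | 43% | 56% | 68% |

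**4. Two readers pooled as if independent (60 vs 60 ratings).** With a common rate p and inter-reader kappa κ, the variance of a patient's two-rating total is 2p(1 − p)(1 + κ), while the test assumes 2p(1 − p). At κ = 0.8 the variance is understated by a factor of 1.8. Simulated Yates size over p = 50-90% is about 4-5% at κ = 0.2, 7-10% at 0.6 and 9-12% at 0.8.

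**The case against.** **For a binary score this is close to a matter of taste.** Yates is a recognised conservative option, coincides here with Fisher's exact test, and never exceeds 5% with one score per patient. The uncorrected test reaches 5.5%. This stands: under the binary reading the plan's choice is defensible, only less powerful.

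**The plan may well mean a binary score.** D.3 uses the plain chi-square for patient characteristics and reserves Yates for image quality, which fits a 2x2 table. That is plausible, but the plan never says so, and the cut would still have to be stated.

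**The power figures rest on invented inputs.** True: scale, distribution and effect are all assumed. They show the direction and rough size of the loss under a consistent shift, not what this trial will see. The reversals show that the rank test is not best for every alternative.

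**Stronger readings that the documents do not support.**

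- A reader might infer that the plan's test simply has a true size of 1-3%. That holds only under the conditions listed in the working.
- A reader might infer that the plan inflates false positives by pooling readers. It does not say that ratings will be pooled; it only fails to exclude it.
- A reader might infer that Aim 1's claim that Dotarem is not inferior is undermined. That aim concerns signal intensity ("To test the hypothesis that the signal intensity enhancement during Dotarem myocardial stress/rest perfusion is relatively constant"), and neither aim states a hypothesis about image quality.

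**Conclusion.** The point holds as a gap in specification with a cheap improvement available; severity is minor. D.3 names a 2x2 test for scores whose scale, cut and unit of analysis are not stated, and the test's behaviour depends on all three:

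- Ordinal, one score per patient: a loss of about 11-24 points of power against Mann-Whitney, for a proportional-odds shift of 3 on the three main assumed scales.
- Binary, one score per patient, assumed two-sided 5% level, common rate 10-90%: size 0.9-2.7%, conservative and acceptable.
- Two readers pooled as independent: size about 4-12%, depending on agreement.

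No reading of the text shows that the comparison is invalid as it will be run. The text does not settle which of these cases applies.

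**What to change.** In D.3:

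1. State the scale and the number of readers. Define one score per patient, derived from the independent readings by a pre-stated rule, for example the mean or median grade or a pre-designated reader. D.2 plans independent ratings, so no consensus session is needed.
2. If the score is ordinal, compare groups with the tie-corrected Mann-Whitney test. Report the probability that a Dotarem image is graded higher than a Gadavist image (ties counted half) with a 95% CI, beside the frequency table that D.3 already plans, which would reveal a difference in spread.
3. If the score is binary, fix the cut before any reading and report the difference in proportions with a 95% CI. Dropping the Yates correction is optional; size can then reach 5.5%.

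The cost is a few sentences, with the same patients, readers and images. Two limits remain. The rank test can miss a difference in spread or at a single cut, as the reversals show. Power also stays low for modest effects: Mann-Whitney has 10-31% at odds ratio 2, depending on the assumed distribution. A non-significant result should therefore not be read as equal image quality, which is why the interval matters.
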